7. EFFICACY, SAFETY, AND PHARMACOKINETIC ASSESSMENTS

For an overview of the study variables and measurement times, see Schedule of Assessments (Table 1).

Variables used to measure treatment compliance with respect to administration of the IMP are described in Section 5.8.

7.1 EFFICACY ASSESSMENTS

Baseline is defined as the seizure frequency during the 6-week Baseline Period.

Retrospective diary data (up to 6 months) will be collected, if available, for an exploratory evaluation of the duration of baseline data capture on interpretation of post-treatment effect.

For all questionnaires and rating scales, the same evaluator (at the clinical site and

Confidential Page 64 of 182

parent/caregiver) will complete the assessments for the duration of the study. Substitutions at the clinic with another rater that has established inter-rater reliability is acceptable on an infrequent basis. For the in-clinic questionnaires and rating scales completed by the parent/caregiver, if the same parent/caregiver cannot complete the questionnaire/rating scale at a visit, the questionnaire/rating scale will not be completed. For the diary, the same parent/caregiver will complete all entries throughout the study.

7.1.1 Seizure Assessments

Seizure frequency by type and duration (<2 minutes, 2-10 minutes, >10 minutes) will be recorded daily by the parent/caregiver in a diary. Seizure types include:

- A: Hemiclonic (note lateralization right body, left body, or independent right and left)
- B: Focal With or Without Retained Awareness
- C: Secondarily Generalized Tonic Clonic (evolving to bilateral convulsive seizure from focal seizure)
- D: Generalized Tonic Clonic Convulsion
- E: Absence or Atypical Absence
- F: Myoclonic
- G: Tonic
- H: Atonic
- I: Clonic
- J: Tonic/Atonic (cannot differentiate)
- K: Infantile Spasms (if under 3 years of age)
- L: Epileptic Spasms (if 3 years of age and older)
- O: Other

Efficacy endpoints that will be derived from the diary data include frequency of convulsive seizures and of all seizures, and the number/duration of seizure free intervals.

Seizures that evolve into SE will be captured by type and duration (>10 minutes) as are all seizures. The diagnosis of SE made by a medical professional should be entered as an SAE if a prolonged seizure or series of seizures persists for 30 minutes or longer, regardless of administration of rescue medication. SE lasting for less than 30 minutes should be entered as an AE, unless one of the other SAE criteria (e.g. hospitalization) are met. If this incident involves multiple seizures close in time, the SE definition applies if the seizures are close together such that consciousness is not regained between ictal events.

Confidential Page 65 of 182

7.1.2 Clinical Global Impression - Improvement

Both the parent/caregiver and the investigator will rate their global impression of the subject's condition throughout the study according to the schedule in Table 1.

The CGI scale measures the change in the subject's clinical status from a specific point in time, i.e., the Baseline Period. The CGI rating scale permits a global evaluation of the subject's improvement over time. The severity of a patient's condition is rated on a 7-point scale ranging from 1 (very much improved) to 7 (very much worse) as follows:

1=very much improved

2=much improved

3=minimally improved

4= no change

5=minimally worse

6=much worse

7=very much worse

The parent/caregiver will be asked to indicate the appropriate response that adequately describes how their child's symptoms have improved or worsened relative to baseline before the beginning of the study (before any study drug was taken).

The investigator will be asked to indicate the appropriate response that adequately describes how the subject's symptoms have improved or worsened relative to baseline before the beginning of the study (before any study drug was taken). A paragraph describing symptoms and function at baseline will be document in the source file prior to rating.

7.1.3 Quality of Life in Childhood Epilepsy Scale

The QOLCE (Appendix 4), a low-burden parent/caregiver completed assessment that looks at how epilepsy affects day-to-day functioning of their child in various life areas, including physical activities, well-being, cognition, social activities, behavior and general health, will be conducted according to the schedule in Table 1. The QOLCE has been validated in children aged 4 and older, and there are published data on the use of the QOLCE in children with epilepsy as young as 2 years of age (Sabaz 2000; Talarska 2007).

The cognitive domain of the QOLCE consists of the following subscales: attention/concentration, memory, languages, and "other cognition". Each of these subscales have shown good internal reliability and consistency (Cronbach's alpha > 0.80) in the population aged 4 and above. The cognitive domain of the QOLCE will be used to assess cognition during study participation in the population aged 5 and older as of the subject's age at baseline.

7.1.4 Pediatric Quality of Life Inventory (PedsQL)

The PedsQL (Appendix 6) is a pediatric modular measure of health-related QoL completed by Confidential

Page 66 of 182

the parent/caregiver on behalf of the subject. It consists of 4 core scales that measure physical, emotional, social, and school functioning. The PedsQL will be conducted according to the schedule in Table 1

7.1.5 Parent/Caregiver Quality of Life

The impact on the quality of life of the parent/caregiver responsible for a patient with DS will be assessed according to the schedule in Table 1 using 3 scales: the EQ-5D-5L, the HADS, and the PedsQL Family Impact Module. Parents/caregivers who do not give consent to collect these ratings scales will not complete them. The same parent/caregiver should complete these ratings throughout the study. If that person is not available at the visit, the scales should not be completed.

The EQ-5D-5L (Appendix 7) is a standardized measure of health status used to provide a simple, generic assessment for clinical and economic appraisal. It consists of 6 questions and can be completed in less than 10 minutes.

The HADS (Appendix 8) is a tool commonly used to determine the levels of anxiety and depression that a person is experiencing. It is a 14-item scale that generates ordinal data. Seven of the items relate to anxiety and 7 relate to depression.

The PedsQL Family Impact module (Appendix 6) is designed to measure the impact of pediatric chronic health conditions on parents and the family by measuring parent self-reported physical, emotional, social, and cognitive functioning, communication, worry, and family daily activities relationships.

The parent/caregiver will be asked to indicate the appropriate response that adequately describes how the care of their child with DS has impacted their quality of life using the scales described above.

7.2 SAFETY ASSESSMENTS

7.2.1 Demographics, Medical/Neurological/Epilepsy History, and Pre-Study Medication

Subject demographics (sex, age, height, weight, and BMI), all ongoing conditions and relevant medical history from the past 5 years (including all major hospitalizations and surgeries) as well as the subject's current medical status will be recorded at the Screening visit. Significant medications taken during the 30 days prior to the Screening visit will be documented.

Medication history will be updated as outlined in Table 1.

7.2.2 Physical Examinations

Complete and abbreviated physical examinations, including height and weight, will be conducted by the investigator or designee during the study as outlined in Table 1. A complete standard of care physical examination for each subject will be performed and will cover the following body systems: general appearance, skin, eyes, ears, nose, throat, heart, lungs, abdomen, neurological

Confidential Page 67 of 182

system, lymph nodes, spine, and extremities. An abbreviated physical examination for each subject will cover the following body systems: heart, lungs, and follow up of other systems as appropriate based on last exam and reported AEs.

Any unfavorable findings not present at screening considered by the investigator as clinically significant, occurring at any point in the study will be documented in the eCRF as an AE.

7.2.3 Neurological Examinations

Complete and abbreviated neurological examination will be conducted by the investigator or designee during the study as outlined in Table 1. A complete standard of care neurological examination for each subject will be performed and will cover the following: eranial nerves, muscle strength and tone, reflexes, coordination, sensory function, and gait. An abbreviated neurological follow-up examination for each subject will evaluate any symptoms or systems found to be abnormal and unstable or potentially unstable that might evolve during study treatment, or to investigate any reported or observed AEs.

Any unfavorable findings not present at screening considered by the investigator as clinically significant, occurring at any point in the study will be documented in the eCRF as an AE.

7.2.4 Vital Signs

Vital signs including blood pressure, heart rate, temperature, and respiratory rate will be documented for subjects during study as outlined in Table 1.

7.2.5 Laboratory Measurements

Laboratory safety parameters will be analyzed using standard validated methods.

The following parameters will be assessed by the laboratory as described in Table 1 and Table 8:

- Hematology: hemoglobin, hematocrit, erythrocytes, erythrocyte mean corpuscular volume, leukocytes, mean corpuscular hemoglobin, mean corpuscular hemoglobin concentration, neutrophils, lymphocytes, monocytes, eosinophils, basophils and platelets
- Blood Biochemistry: albumin (ALB), alkaline phosphatase (AP), alanine aminotransferase (ALT; SGPT), aspartate aminotransferase (AST; SGOT), bicarbonate, blood urea nitrogen (BUN), calcium (Ca), carbon dioxide (CO₂), chloride (Cl), creatinine, creatine kinase, gamma-glutamyl transferase (GGT), globulin, glucose, lactate dehydrogenase (LDH), phosphorus, potassium (K), sodium (Na), thyroid function (T3, T4, and thyroid stimulating hormone [TSH]), total bilirubin, direct bilirubin, total cholesterol, total protein, triglycerides, uric acid.
- Tests of growth and precocious puberty: Growth hormone (GH), insulin-like growth factor-1 (IGF-1, low sensitivity), prolactin, Luteinizing Hormone (LH), Follicle

Confidential Page 68 of 182

Stimulating Hormone (FSH), testosterone, estradiol

- Epilepsy genotype panel
- Coagulation: Prothrombin time (PT)/International normalized ratio (INR), activated partial thromboplastin time (PTT)
- Whole blood cannabidiol
- Urinalysis: analysis for pH, glucose, ketones, nitrite, protein, bilirubin, urobilinogen, leukocyte esterase, and occult blood. Microscopic analysis will be performed for blood, all cell types, and casts.
- Urine pregnancy test: Urine pregnancy testing will be performed in female subjects of childbearing potential.
- Urine THC panel
- The investigator will receive the laboratory report from the central laboratory. After reviewing the report and evaluating any results that are outside the normal range, the investigator must sign and date the laboratory report.

Tests resulting in abnormal laboratory values that have been classified by the investigator as abnormal, clinically significant should be repeated as soon as possible after receiving the laboratory report to rule out laboratory errors.

At Screening, any laboratory values that deviate from the reference ranges and are considered by the investigator as clinically relevant must be documented on the medical history form of the eCRF. Any deviation outside of the reference range considered by the investigator as clinically significant (i.e., classified as an abnormal, clinically significant value) at any visit after screening will be documented in the eCRF as an AE (see Section 9).

7.2.6 Plasma Sample for Concomitant Antiepileptic Drug(s)

Plasma samples to ensure that concomitant antiepileptic drug(s) (AEDs) dosing is within an acceptable range will be conducted during the study as outlined in Table 1. Samples collected at Visit 6 will be analyzed after collection as a safety measure. Samples collected at other time points will be analyzed at study end and do not constitute safety assessments.

7.2.7 Electrocardiograms

Twelve-lead ECGs will be conducted during study as outlined in Table 1 after the subject has been in the supine position resting for ≥5 minutes. Heart rate, PR duration, QRS duration, QT duration, QTcF (Fridericia's correction formula), and the investigator's overall interpretation will be recorded.

Confidential Page 69 of 182

7.2.8 Doppler Echocardiography

Doppler echocardiography will be conducted at a facility with experience for the subject's age during study as outlined in Table 1. Doppler echocardiography uses ultrasound technology to examine the heart or blood vessels. An ECHO uses high frequency sound waves to create an image of the heart while the use of Doppler technology allows determination of the speed and direction of blood flow by utilizing the Doppler effect. Predetermined standard guidelines on the proper evaluation of certain measurements, as well as abnormality thresholds, were constructed by the sponsor's IPCAB prior to study initiation. These thresholds are provided in Table 10 (Adverse Events of Special Interest). A manual of proper ECHO technique for sites is provided in a separate document.

7.2.9 Tanner Staging

Tanner Staging (Appendix 5) will be assessed for subjects >7 years old during the study as outlined in Table 1. Conceptually, pubertal maturation can be described in terms of sequence, timing, and tempo. Puberty consists of a series of predictable events, and the sequence of changes in secondary sexual characteristics has been categorized by several groups. The staging system used most frequently was published by Marshall and Tanner (1969, 1970) and the sequence of changes are commonly referred to as 'Tanner stages'.

7.2.10 Columbia-Suicide Severity Rating Scale

C-SSRS (Appendix 2) will be assessed during study as outlined in Table 1. The C-SSRS is a validated rating scale that assesses suicidal behavior and ideation. The scale is used to assess and track suicide events and provides a summary measure of suicidal tendency. The C-SSRS version 6/23/10 (Children's Baseline/Screening and Children's Since Last Visit) will be used in this study as appropriate for the age and level of intellectual development.

Subjects who are younger than 7 years chronologically, or who are judged by the investigator not to have the mental capacity to understand the questions as specified on the C-SSRS, will not complete the rating. The investigator should use his/her judgment to substitute intellectually-appropriate questions to probe the tendency for self-harm.

If a subject with the intellectual capacity to complete the C-SSRS has their 7th birthday during the study, use of the C-SSRS should be initiated at subsequent visits.

7.2.11 Adverse Events

Adverse events will be collected from the time of signing the informed consent form/assent form until the end of the study, including the follow-up clinic visit. Details of the definitions and categorization of AEs, and procedures for the reporting of AEs, are available in Section 9.

Severity and causality of AEs will be evaluated according to the criteria specified in Section 8.2 and Section 8.3, respectively. The observation period for AE reporting is specified in

Section 8.4. At the beginning of each visit at the study site, the study personnel will specifically Confidential

Page 70 of 182

inquire about any AEs that might have occurred since the last study site visit. All AEs will be recorded on the appropriate eCRF page.

7.2.12 Behavior Rating Inventory of Executive Function (BRIEF)

The BRIEF is a standardized, validated rating scale to measure executive function in children ages 2-18within the home and school environments; it will be assessed according to the schedule in Table 1. The BRIEF measures multiple aspects of executive functioning; scales include Inhibit (control impulses; stop behavior), Shift (move freely from one activity/situation to another; transition; problem-solving flexibility), Emotional Control (modulate emotional responses appropriately), Initiate (begin activity; generate ideas), Working Memory (hold information in mind for purpose of completing task), and Plan/Organize/Organization of Materials (anticipate future events; set goals; develop steps; grasp main ideas), and Monitor (check work; assess own performance).

7.3 PHARMACOKINETIC ASSESSMENTS

Blood samples for PK assessments of fenfluramine and its metabolite (norfenfluramine) will be obtained from all subjects via an indwelling cannula or by venipuncture.

Blood samples for PK assessment (2 mL) will be obtained at the following time points:

• Maintenance Period Study Day 43: within 1 hour prior to the morning dose, and 1, 2, and 4-6 hours after the morning dose.

A total of 4 PK samples will be drawn for each subject for a total of approximately 8 mL of blood.

When blood draws for PK coincide with other assessments, the PK draws take precedence.

The procedure for the collection and handling of PK samples is outlined in a separate study manual.

7.4 APPROPRIATENESS OF MEASUREMENTS

All of the variables assessed are standard tests or procedures that are commonly used in studies of this type.

8. ADVERSE EVENTS

8.1 **DEFINITIONS**

8.1.1 Adverse Events

According to ICH guidelines, an AE is any untoward medical occurrence in a patient or clinical investigation subject administered a pharmaceutical product and which does not necessarily have a causal relationship with this treatment. An AE can, therefore, be any unfavorable and unintended sign (including an abnormal, clinically significant laboratory finding), symptom, or disease

Confidential Page 71 of 182

temporally associated with the use of a medicinal (investigational) product, whether or not considered related to the medicinal (investigational) product. The period of observation for adverse events extends from the time the subject gives informed consent until the end of study.

Adverse events may include:

- Exacerbation (i.e., an increase in the frequency or severity) of a pre-existing condition. Illness present before study entry should be recorded in the medical history section of the eCRF and only be reported as an AE if there is an increase in the frequency or severity of the condition during the study. Exacerbation of seizures is considered an AE if there was an increase in frequency beyond the subject's typical pre-study fluctuations, or in the event that seizures lengthen in duration in a clinically meaningful way compared with baseline, or if a new seizure type emerges.
- A clinical event occurring after consent but before IMP administration.
- Intercurrent illnesses with an onset after administration of IMP.

Adverse events do not include:

- Medical or surgical procedures (the condition that leads to the procedure is the AE, e.g., tonsillitis is the AE if a tonsillectomy is performed)
- Situations where an untoward medical occurrence has not taken place. For example:
 - Planned hospitalizations due to pre-existing conditions, which have not worsened.
 - Hospitalizations that occur for procedures not due to an AE (e.g., cosmetic surgery).
 - o Hospitalizations for a diagnostic procedure where the hospital stay is less than 24 hours in duration or for normal management procedures (e.g., chemotherapy).

For laboratory safety parameters, any instances of absolute values being outside the reference range or changes at any visit after study start that are considered by the investigator as clinically significant must be recorded in the eCRF as AEs. In addition, at the investigator's discretion, any changes or trends over time in laboratory parameters can be recorded in the eCRF as AEs if such changes or trends are considered to be clinically relevant, even if the absolute values are within the reference range.

Laboratory findings do not need to be reported as AEs in the following cases:

- 1. Laboratory parameters are already beyond the reference range, unless a further increase/decrease can be considered an exacerbation of a pre-existing condition.
- 2. Abnormal laboratory parameters caused by mechanical or physical influences on the blood sample (e.g., hemolysis) and flagged as such by the laboratory in the laboratory report.
- 3. Abnormal parameters that are obviously biologically implausible (e.g., values that

Confidential Page 72 of 182

- are incompatible with life).
- 4. An abnormal laboratory value that cannot be confirmed after a repeated analysis, preferably in the same laboratory (e.g., the previous result could be marked as not valid and should not necessarily be reported as an AE).

8.1.2 Serious Adverse Events

A serious adverse event (SAE) is defined as any untoward medical occurrence that at any dose:

- 1. **Results in death** The event must be the cause of death for the SAE to meet this serious criterion.
- 2. **Is life-threatening** The term "life-threatening" refers to an event in which the subject was at risk of death at the time of the event; it does not refer to an event that hypothetically might have caused death if it had been more severe.
- 3. Requires in-patient hospitalization or prolongation of existing hospitalization The sponsor considers "hospitalization or prolongation of existing hospitalization" for at least 24 hours as the defining criterion for an SAE. Hospital admissions for planned surgery or for normal disease management procedures (e.g., chemotherapy) are not considered as defining criteria for SAEs.
- 4. Results in persistent or significant disability or incapacity.
- 5. Is a congenital anomaly or birth defect.
- 6. **Is medically significant** A medically significant event is defined as an event that does not meet any of the other 5 SAE criteria, but which is judged by a physician to potentially jeopardize the subject or require medical or surgical intervention to prevent one of the above outcomes listed as an SAE criterion. Anaphylaxis that is successfully treated by administration of epinephrine prior to other sequelae is an example of a potentially medically important event.

For the purpose of data collection in this study, a prolonged seizure or series of seizures from which the subject does not regain consciousness between ictal events, that is at least 30 minutes in duration, is termed status epilepticus (SE). A single episode of SE in a 24-hour period, regardless of whether rescue medication was administered, should be entered in the AE log as well as in the seizure diary. If two or more episodes occur within 24 hours, each lasting 30 minutes or more, an SAE of SE should be recorded. Hospitalization to manage SE, regardless of the number of episodes, should be reported as an SAE.

Adverse events that do not fall into the above categories are defined as nonserious AEs.

8.1.3 Adverse Events of Special Interest

As per ICH guidance (E2F Development Safety Update Report [2011]), the sponsor has identified the following AESIs for the ZX008 program (Table 10).

Confidential Page 73 of 182

Table 10: Adverse Events of Special Interest

CV/Respiratory

- 1. Chest pain any pain in sternal area that is described for example as crushing, burning, sharp, stabbing or dull.
- 2. Dyspnea/shortness of breath any signs of difficult or labored breathing unrelated to a previous medical condition that has not worsened.
- 3. Persistent cough longer than 4 weeks without a confirmed identified pathogen (or any other persistent cough that the investigator feels is suspicious).
- 4. Increase in blood pressure >30% from Screening blood pressure or a systolic pressure ≥140 mmHg after repeated measures during one visit. Blood pressure should be repeated at appropriate times within the visit.
- 5. Jugular venous distention-visible bulging of the external jugular veins on either side of the neck
- 6. New onset heart murmur
- 7. Pulmonary rales an abnormal respiratory sound heard during auscultation of the lungs, which is also described as a crackle.
- 8. Tachycardia a persistent HR >30% above the screening value and unrelated to exercise, exertion or anxiety. Heart rate should be repeated at appropriate times within the visit.
- 9. Signs that could indicate right ventricular failure:

Peripheral edema

Ascites

Syncope

Decompensated right ventricular failure – symptoms include shortness of breath, frequent coughing especially when lying flat, abdominal swelling and pain, dizziness, fainting, and fatigue

10. Signs on ECHO indicative of potential valvulopathy

valve regurgitation (aortic or mitral)

moderate or severe valve regurgitation (tricuspid or pulmonary)

Mean Mitral valve gradient ≥ 4 mmHg

Mean Aortic valve gradient ≥ 15 mmHg

Mean Tricuspid valve gradient ≥ 4 mmHg

Peak Pulmonary valve gradient ≥ 21 mmHg

11. Signs on ECHO indicative of pulmonary hypertension

- a. Tricuspid Regurgitation Jet velocity > 2.8 msec with or without the following findings OR
- b. One of the following findings in the absence of being able to measure Tricuspid Regurgitation Jet velocity:
 - 1. Change in right ventricle/left ventricle basal diameter ratio > 1.0
 - ii. Right ventricular acceleration time < 100 msec
 - iii. Dilatation of the inferior caval vein (diameter>21 mm and <50% inspiratory decrease) and/or right atrium
 - iv. Change in the geometry of the interventricular septum in systole (flattening) with left ventricular eccentricity index >1.1 in systole and/or in diastole
 - v. Early diastolic pulmonary regurgitation velocity > 2.2 m/sec
 - vi. Tricuspid Anular Plane Systolic Excursion below 18 mm or below Z-score –2

continued

Confidential Page 74 of 182

Table 10: Adverse Events of Special Interest (continued)

aut 10	. Maveise Events of Special Interest (continued)			
Metabolic/Endocrine				
1.	Elevated prolactin level ≥2x above the upper limit of normal (ULN)			
2.	Galactorrhea			
3.	Gynecomastia			
4.	Increase in fasting serum blood glucose ≥2x ULN			
5.	Hypoglycemia – serum blood glucose more than 20% below the glucose level on Study Day -1			
	value or more than 10% below LLN (reference range 60 – 140 mg/dL)			
Neuropsychiatric				
1.	Serotonin syndrome (At least 3 of following symptoms must be present: Agitation,			
	restlessness, confusion, both increased HR and blood pressure, dilated pupils, muscle			
	twitching, muscle rigidity, hyperhidrosis, diarrhea, headache, shivering, tremors, both nausea			
	and vomiting)			
2.	Hallucinations			
3.	Psychosis			
4.	Euphoria			
5.	Mood disorders: depression and anxiety if they rise to a level of a disorder			
6.	Suicidal thoughts, ideation or gestures			
Genitourinary				
1.	Priapism			

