4.1 INCLUSION CRITERIA

Subjects meeting all of the following inclusion criteria may be enrolled into the study:

- 1. Subject is male or non-pregnant, non-lactating female, age 2 to 18 years, inclusive as of the day of the Screening Visit. Female subjects of childbearing potential must not be pregnant or breast-feeding. Female subjects of childbearing potential must have a negative urine pregnancy test. Subjects of childbearing or child-fathering potential must be willing to use medically acceptable forms of birth control (see Section 4.4), which includes abstinence, while being treated on this study and for 90 days after the last dose of study drug.
- 2. Subject must have documented medical history to support a clinical diagnosis of Dravet syndrome, where convulsive seizures are not completely controlled by current antiepileptic drugs.
- 3. Subjects must meet all of the following 5 criteria:
 - a. Onset of seizures in the first year of life in an otherwise healthy infant.
 - b. A history of seizures that are either generalized tonic-clonic or unilateral clonic or bilateral clonic, and are prolonged.
 - c. Initial development is normal.
 - d. History of normal brain MRI without cortical brain malformation.
 - e. Lack of alternative diagnosis.
- 4. Subjects must meet at least one of the following 3 criteria:
 - a. Emergence of another seizure type, including myoclonic, generalized tonic-clonic, tonic, atonic, absence and/or focal has developed after the first seizure type.
 - b. Prolonged exposure to warm temperatures induces seizures and/or seizures are associated with fevers due to illness or vaccines, hot baths, high levels of activity and sudden temperature changes and/or seizures are induced by strong natural and/or fluorescent lighting, as well as certain visual patterns.
 - c. Genetic test results consistent with a diagnosis of Dravet syndrome (pathogenic, likely pathogenic, variant of unknown significance, or inconclusive but unlikely to support an alternative diagnosis.)
- Subject must have had ≥4 convulsive seizures (tonic, tonic-atonic, tonic-clonic, clonic) per 4-week period for past 12 weeks prior to screening, by parent/guardian report to investigator or investigator medical notes.
- 6. All medications or interventions for epilepsy (including KD and VNS) must be stable for at least 4 weeks prior to screening and are expected to remain stable throughout the study.

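### Table 10 puts the 1.0 limit for right/left ventricular diameter ratio on the change rather than the ratio; secondarily, the 18 mm TAPSE limit has no age or size condition

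*Protocol*

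**What the plan says.** Section 7.2.8 says that the cardiac advisory board (IPCAB) set the echocardiographic abnormality thresholds before the study began and that they are given in Table 10. The separate manual it mentions covers ECHO technique.

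In Table 10, item 11 of the CV/Respiratory list covers signs of pulmonary hypertension. Part a is a limit on tricuspid regurgitation jet velocity. Part b is the alternative: "One of the following findings in the absence of being able to measure Tricuspid Regurgitation Jet velocity". Six signs follow. Three matter here:

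- Sign i: "Change in right ventricle/left ventricle basal diameter ratio > 1.0".
- Sign iv, on flattening of the septum, opens with the same word, change, but then sets an absolute limit: "with left ventricular eccentricity index >1.1 in systole and/or in diastole".
- Sign vi: "Tricuspid Anular Plane Systolic Excursion below 18 mm or below Z-score" of −2.

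Other items in the same table that rest on a change name their reference: "Increase in blood pressure >30% from Screening blood pressure", "a persistent HR >30% above the screening value" and, for glucose, "more than 20% below the glucose level on Study Day -1".

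Section 4.1 admits subjects of "age 2 to 18 years, inclusive as of the day of the Screening Visit". Under Section 3.7.2, a pediatric cardiologist reads all ECHOs centrally, a case that meets a pre-defined threshold goes to the IPCAB for secondary adjudication, and IPCAB members audit ECHOs read as normal.

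**The concern.** These lines are decision limits. Section 1.2 names pulmonary hypertension as one of the two reasons fenfluramine products were withdrawn in the USA, so this is a core safety definition.

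Sign i attaches 1.0 to the change in a ratio. A reader who applies it as written needs a rise of more than 1.0, a far higher bar than a ratio above 1.0, and would pass over ratios in between. The sign also does not say which ECHO the change is measured from. The table's blood pressure, heart rate and glucose items do name a reference, and Section 8.9.1 uses yet another comparator, the last reading, for stepping up oversight.

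Sign vi errs, if at all, in the other direction. It joins a fixed length and a Z-score with an unqualified or, in subjects from 2 to 18 years old. The fixed length can then override a Z-score that the protocol itself treats as within limits.

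At stake is whether an ECHO without a measurable jet is flagged as an adverse event of special interest and referred to the IPCAB.

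**Working it through.** The protocol gives no figure to reproduce here: it states no usual ventricular diameter ratio, no TAPSE norms and no share of ECHOs without a measurable jet. The check is arithmetic on an assumed ratio for sign i and set logic for sign vi.

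**Sign i.** Inputs: the limit 1.0, from Table 10, and a pre-treatment ratio r. The value of r is an assumption: 0.7, with a range of 0.6 to 0.9.

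- As written (change above 1.0): the ECHO must show a ratio above r + 1.0, a relative rise of more than 1.0/r.
- As an absolute limit (ratio above 1.0): the relative rise needed is more than (1.0 − r)/r.
- Band missed by the wording: above 1.0, up to 1.0 + r.

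| Assumed r | Ratio needed as written | Rise needed | Ratio needed, absolute | Rise needed | Missed band |
|---|---|---|---|---|---|
| 0.6 | above 1.6 | above 167% | above 1.0 | above 67% | above 1.0 to 1.6 |
| 0.7 | above 1.7 | above 143% | above 1.0 | above 43% | above 1.0 to 1.7 |
| 0.9 | above 1.9 | above 111% | above 1.0 | above 11% | above 1.0 to 1.9 |

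Example: a child who goes from 0.7 to 1.5 has a change of 1.5 − 0.7 = 0.8. That does not exceed 1.0, so sign i as written is not met, although the ratio is well above 1.0.

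Which reading is meant? Sign iv has the same opening and a plainly absolute limit, which points to an absolute limit in sign i as well. But in sign iv the number is attached to a named index, whereas in sign i nothing stands between the word change and the 1.0. No other section supplies the absolute reading.

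**Sign vi.** Where a Z-score can be computed, the children whom the 18 mm limb adds are

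{TAPSE < 18 mm or Z < −2} minus {Z < −2} = {TAPSE < 18 mm and Z ≥ −2}.

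Every child added therefore has a Z-score of −2 or higher, and a Z-score within the limit can never spare a child below 18 mm. This follows from the wording alone. The size of the added set does not: it depends on TAPSE norms by age or size, and it may be empty. Where no Z-score can be computed, the 18 mm limb is the only limit available and has a proper function.

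**The case against.** The strongest reply is that neither line causes harm in practice. An experienced pediatric cardiologist reads every ECHO and would take sign i as an absolute limit, as sign iv suggests. If a ratio were passed over, any one of the other five signs would be enough, unexpected cardiac events also go to the IPCAB, and IPCAB members audit normal readings. For sign vi, a sensitive trigger is defensible for this drug: meeting it leads to adjudication, not discontinuation, and under footnote b of Table 7 extended follow-up for a pulmonary hypertension sign depends on that adjudication. The IPCAB manual, which is not at hand, may hold further procedure.

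Much of this stands, and it sets the severity. It does not make sign i correct. Section 7.2.8 places the thresholds in Table 10, and a limit that works only if the reader departs from its wording should be reworded.

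Four stronger readings are tempting and are not supported:

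- *Many healthy young children would be flagged by sign vi.* This needs norms the protocol does not give. With normally distributed TAPSE, assumed means of 14 to 26 mm and SDs of 1.5 to 3 mm, the flagged share of healthy children runs from 2.3%, the same as by Z-score alone, to 99.6%. The assumption decides the answer.
- *Children would be wrongly kept out of the trial.* Randomization criterion 2 in Section 4.3 bars signs of pulmonary hypertension and requires the central reader's approval, but it does not cite Table 10. An effect on entry is only inferred.
- *Sign i is uniquely unusable at screening.* The heart rate item and the percentage limb of the blood pressure item cannot register a change from screening at screening either.
- *The missing reference ECHO leaves sign i without any comparator.* Table 1 schedules one pre-treatment ECHO, at Screening, which is a natural reference. The text simply does not say so.

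**Conclusion.** The point holds, at low severity. The main fault is sign i: as written, its limit falls on the change. With an assumed pre-treatment ratio of 0.7 (range 0.6 to 0.9), it would miss ratios above 1.0 and up to 1.7 (1.6 to 1.9). The exact upper end rests on that assumption; the direction does not, because for any positive pre-treatment ratio the written limit lies above 1.0.

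Sign vi is a secondary, logical flaw. Its 18 mm limb, where a Z-score exists, can add only children within the protocol's own −2 limit, in a number that cannot be derived and may be zero.

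Both apply only to ECHOs without a measurable tricuspid jet, and both act only on event flagging and IPCAB referral. A reader might infer that the efficacy results or the comparison between arms are at risk; nothing in the protocol links these thresholds to either.

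**What to change.** Reword two lines of Table 10, item 11.b.

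- Sign i: drop the word change, so that the sign is a right-to-left ventricular basal diameter ratio above 1.0. This is the absolute form of limit that sign iv already uses, and it removes the need for a reference ECHO.
- Sign vi: use TAPSE Z-score below −2 wherever a Z-score can be computed. Apply 18 mm only to adult-sized subjects, with the size cut-off set by the IPCAB, or where no Z-score is available.

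The cost is two reworded lines and one cut-off from the IPCAB. No new measurement is needed, since the ratio and the Z-score are already in the table. The downside is a slightly less sensitive referral trigger for small children under sign vi. Keeping 18 mm as a fallback means that a small child without a Z-score can still be flagged by the fixed length. That is acceptable, because no other TAPSE limit is then available.
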